#### Visit 2: For Participants in whom a skin biopsy was recommended by the telemedicine team (Day 7+/-2)

- Perform skin biopsy
- If a biopsy is performed, the participant is given at-home instructions for wound care (Supplement R) and the expected wait time for the biopsy results

- Follow-up care to the skin biopsy will proceed the same as standard clinical practice with Visits 4 and 5

#### **Phone Call For Participants with Skin Biopsy after Tele Dermatologist recommendation (Day 17+/-3)**

- Record adverse events as reported by participant
- Communicate biopsy pathological report results and medical advice for next steps if needed or reassurance (Supplement S)
- Ask about symptoms and signs of wound healing progression

#### **Optional Visit 3: Wound Check for biopsy site performed on Visit 2 (Day 21+/-3)**

- Check site of biopsy for healing and any AEs
- Communicate medical advice for next steps if necessary.

#### **7.3.4 Study Completion**

Once all lesions have been evaluated, all biopsy results have been communicated, and all wounds are healing well, participants will be given a study completion questionnaire (Supplement L) regarding his/her overall experience in the study. At this point, participation in the study is complete.

#### **7.3.5 Withdrawal/Early Termination Visit**

Participants may withdraw at any time by contacting the DCSU staff via phone call or in-person. For participants who did not undergo a skin biopsy, no follow-up care is needed. Participants who underwent a skin biopsy will be offered a final visit to communicate biopsy results, and for a wound check or suture removal if needed. They will also receive a referral to the NYU Skin & Cancer clinic for follow up care if needed. Any adverse events will also be recorded.

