At the DCSU, study participants: 1) will be informed of the details of the study and given time to review the IRB approved Informed Consent form; 2) given the opportunity to ask questions; and 3) will be enrolled after signing an informed consent form (ICF) in a private encounter. After the participant consenting process, lesion eligibility will be confirmed by the study team, and participants will provide the study team with contact information, demographic information, past medical history of skin cancer, family history of skin cancer, natural hair color, eye color, likelihood of burning with unprotected sun exposure, likelihood of tanning with unprotected sun exposure, tanning bed exposure, moderate to severe sunburn exposure, history of atypical or dysplastic nevi, estimate of number of moles on body, estimate of number of freckles on face, and identification of up to three lesions (location, onset, quality, and prior treatment) by completing the Enrollment Questionnaire (Supplement K). Study personnel will have access to these data in order to contact participants for follow up communications including the telemedicine report, biopsy results, wound healing check, scheduling, and administering the study completion questionnaire. Study personnel will also have access to telemedicine data on each participant including clinical images, dermoscopic images, and Nevisense scores. Information about participants will be recorded either on source documents or directly into REDCap depending on what is more convenient for the study team and on whether there are temporary technological barriers to direct REDCap documentation. Any source documents will be kept in the patient's study binder and file cabinets at DCSU. The data will later be entered into the REDCap database case report forms. Only study personnel will have access to the source documents and the REDCAP forms. Study participants will be assigned a participant study ID number.

In total, the study requires participant involvement for about 1-4 weeks, depending on whether a biopsy is recommended and the participant's availability. Retention measures include calling participants 3 separate times to ensure a return visit for biopsy (if recommended), to communicate teledermatology and/or biopsy results and check wound healing, and/or to

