conduct the study completion questionnaire. In the event of three failed attempts to reach the participant regarding biopsy results, the participant will be sent a certified letter communicating the biopsy results and need for follow-up medical care (if needed) (Supplement F). In the event that we are unable to make contact with the subject to communicate the teledermatology recommendation, we will send a certified letter with the recommendation printed (Supplement G). ). In the event that the teledermatology team recommends a biopsy and a participant cannot be contacted to schedule the biopsy or does not show up for a scheduled biopsy appointment, we will send a certified letter instructing them to contact us (Supplement H). At any point during the participant's involvement in the study, they can reach the DCSU by telephone to contact study personnel with concerns regarding wound healing, results interpretation, etc. Medical issues will be referred to one of the physician site investigators (e.g. dermatology resident or attending medical monitor). For emergencies, participants may contact [name] with information provided in the emergency card. (Supplement H)

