#### **5.7.2 Handling of Participant Withdrawals or Termination**

Participants can withdraw voluntarily at any time during the study. If a participant withdraws prior to receiving a recommendation to have their lesion(s) biopsied, the biopsy will not take place. However, in the interest of participant safety, we will attempt to contact the participant on 3 separate occasions and, if needed, send a certified letter to deliver the biopsy recommendation (Supplement G). If a participant withdraws after biopsy is conducted but before the pathology results are available, all efforts to contact the participant with results and check on wound healing will continue. In the unlikely event that a participant presents with a clinically obvious melanoma (for which a biopsy would be recommended) and chooses to withdraw prior to completing the evaluation and/or undergoing a biopsy, we will still recommend a biopsy to this participant and will facilitate an appointment in our clinic if participant is amenable.

In the event of a significant number of withdrawals or terminations and enrollment has already closed, enrollment will re-open to capture 500 participants.

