### 7.3.2 Enrollment/Baseline

#### Enrollment/Initial Visit (Visit 1, Day 1)

- Participant and lesion eligibility confirmed by study personnel
  - This is the formal study screening prior to official enrollment (i.e. signing informed consent)
- Participant given Key Information Sheet with an overview of the study (Supplement Q)
- Conduct informed consent procedure and obtain signed ICF, if not conducted electronically prior to visit
- Assign subject ID for participant
- Obtain demographic information, medical history, medication history as part of enrollment questionnaire (Supplement K). If not conducted electronically prior to visit
- Acquire clinical images, dermoscopic image, and Nevisense data for each lesion
  - Nevisense procedure: the lesion is cleansed with an alcohol wipe and the electrical impedance measurement is conducted using a spring-loaded probe and disposable electrode measuring 5mm x 5mm. The measurement takes <1 minute and the electrical impedance score (EIS) will be recorded. Larger lesions may require a second measurement at another location within the lesion.
  - Record any adverse events from the procedure
  - Neither participants nor the in-person dermatologist will be aware of the score.
- Study team will number the skin lesions using Devon Skin Marker to verify same lesion evaluated across all assessments including the in person dermatologist
- Fill out questionnaire assessing telemedicine evaluation experience so far (Supplement L)
- In-person dermatologist examination of lesion(s) using naked eye and dermoscopy
- If a biopsy is recommended by the in-person dermatologist, participant will be offered a skin biopsy procedure or offered a second appointment within 1-2 weeks for the biopsy procedure
  - If a biopsy is performed, the participant is given at-home instructions for wound care (Supplement R) and the expected wait time for the biopsy results
  - Alternatively, the participant can choose to have the procedure done at another facility. The signed ICF includes permission for the study team to obtain those medical records
  - Follow-up care to the skin biopsy will proceed per standard clinical practice and includes result communication, wound care monitoring, suture removal if applicable and recommendations for follow-up care.
- If a biopsy is not recommended by the in-person dermatologist, the participant is given the expected wait time for telemedicine recommendation phone call.

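### The missed-biopsy letter (5.4) and the clinic referral at withdrawal (7.3.5) leave out a few participants whose recommended biopsy was never done

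*Combined protocol and SAP*

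**What the plan says.** **Withdrawal.** Section 7.3.5 divides withdrawers by whether a biopsy was done. For those without one: "For participants who did not undergo a skin biopsy, no follow-up care is needed". Those with one are offered a final visit for results, wound check or suture removal, and of them it says "They will also receive a referral to the NYU Skin & Cancer clinic for follow up care if needed".

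Section 5.7.2 handles three cases:

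- The recommendation has not yet been received. "If a participant withdraws prior to receiving a recommendation to have their lesion(s) biopsied, the biopsy will not take place", but three contact attempts and, if needed, a certified letter deliver the recommendation.
- The biopsy was done and pathology is pending. Contact efforts continue.
- The lesion is a clinically obvious melanoma. Here "we will still recommend a biopsy to this participant and will facilitate an appointment in our clinic if participant is amenable".

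**Missed biopsy.** Under 7.3.2, when the in-person dermatologist recommends a biopsy, the "participant will be offered a skin biopsy procedure or offered a second appointment within 1-2 weeks for the biopsy procedure". Section 5.4 provides three calls to secure a return visit for any recommended biopsy. Its certified letter has a narrower trigger: "In the event that the teledermatology team recommends a biopsy and a participant cannot be contacted to schedule the biopsy or does not show up".

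**The concern.** The protocol already treats an unresolved biopsy recommendation as something to pursue. It writes to withdrawers who have not heard their recommendation, and to teledermatology patients who miss the biopsy. Section 2.4.1 gives the reason: leaving a suspicious lesion under observation risks growth and later-stage diagnosis.

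Two groups in much the same position fall outside the wording. One is the participant with a deferred in-person recommended biopsy who does not come back. The other is the participant who has been told to have a biopsy, for a lesion that is suspicious but not obviously melanoma, and formally withdraws first. At stake is a small chance that a skin cancer goes undiagnosed for want of a letter or referral that the protocol already gives to similar people.

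**Working it through.** This is mainly a comparison of text. The arithmetic only sets the scale, and the plan has no figure of its own to reproduce.

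**Step 1: is there an interval between recommendation and biopsy?** Yes, by both routes. In person, the biopsy can be deferred 1-2 weeks (7.3.2). By telemedicine, the call is on Day 4 ± 2 and the biopsy visit on Day 7 ± 2 (7.3.3).

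**Step 2: which rule applies in that interval?**

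| Situation, biopsy not done | Rule | Provision |
|---|---|---|
| Withdraws, recommendation not yet received | 5.7.2 | Three contacts, then certified letter |
| Withdraws, clinically obvious melanoma | 5.7.2 | Recommendation repeated, appointment facilitated |
| Withdraws, recommendation received, other suspicious lesion | None in 5.7.2; no referral in 7.3.5 | None at withdrawal |
| Unreachable or no-show, teledermatology recommendation | 5.4 | Three calls, then certified letter |
| Unreachable or no-show, in-person recommendation | 5.4 | Three calls; letter not clearly triggered |

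The last row says *not clearly* because the teledermatology team reads every lesion and may also have recommended biopsy. But where the in-person dermatologist has recommended biopsy, 7.3 withholds the team's recommendation from the participant. The study-design schematic (footnote 2) sends no telemedicine report when all eligible lesions were recommended for biopsy in person. Whether an uncommunicated team recommendation sets off the letter is left open.

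Section 15.3 counts failure to follow a biopsy recommendation among the ways of leaving the study, but attaches only a payment consequence.

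**Step 3: number of withdrawers in the third row.** Inputs:

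- 500 participants (5.6).
- 1% withdrawal (10.4).
- Recommendation rate per participant of 10% to 20%. The lower value is the share expected to undergo biopsy (2.4.1). The upper value comes from the 50-100 recommended biopsies in 10.4: 100 / 500 = 20% if no participant has more than one.

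Results:

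- Withdrawals: 500 × 1% = 5.
- Withdrawal independent of recommendation: 5 × 10% = 0.5 to 5 × 20% = 1.0.
- Every withdrawal follows a recommendation: 5.

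None of these subtracts people already biopsied, people still awaiting their recommendation, or obvious melanomas.

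**Step 4: cancers among them, under independence.** With about 2% of subjects malignant (2.4.2), 5 × 2% = 0.1. With the 29:1 benign-to-malignant ratio in 14.3, 0.5 × 1/30 ≈ 0.02 to 1.0 × 1/30 ≈ 0.03. The range is therefore about 0.02 to 0.1.

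**Step 5: no-shows missing the letter.** Section 10.4 expects 2% lost to follow-up: 500 × 2% = 10. But 10.3.5 defines that group to include people missed only for a wound check or the completion questionnaire. The share with an outstanding biopsy recommended in person is not given, so no count can be derived.

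**The case against.** The strongest reply is that the withdrawer has already been well served. The recommendation was delivered, a biopsy at the study unit was offered at no cost (15.2), another facility was named as an alternative (7.3.2, 7.3.3), and 5.4 adds calls for those due to return. A referral at withdrawal is a further route to a biopsy the person chose not to have. This stands, and it limits the point to the missing referral. A reader might infer that people leave unaware of a possible cancer; the documents do not support that.

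A reader might also infer that 7.3.5 contradicts 5.7.2. Section 7.3.2 describes the aftercare this way: "Follow-up care to the skin biopsy will proceed per standard clinical practice and includes result communication, wound care monitoring, suture removal if applicable". If 7.3.5 uses the phrase in that sense, its sentence is correct, since someone without a biopsy needs no biopsy aftercare. The referral is still restricted to biopsied withdrawers on either reading, so the gap remains but the contradiction is not established.

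On the letter, the reply is that any one of the teledermatologists can trigger a biopsy recommendation, and 10.3.2 expects agreement and sensitivity close to one, so few recommendations would be in-person only. That reduces the number affected. It does not settle the wording, because the team's recommendation is withheld when the in-person dermatologist has already recommended biopsy.

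Finally, the phone scripts and sample letters are supplements that are not shown and may partly cover these cases. Section 5.4 cites Supplement H for the missed-biopsy letter, but Section 19 lists H as the emergency card, so the letter itself cannot be checked.

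**Conclusion.** The point holds as a minor participant-safety gap in two sections. Both are stated rules with too narrow a scope.

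The expected number of affected withdrawers is about 0.5 to 1, assuming 1% withdrawal, a 10-20% recommendation rate and independence between the two. It could reach 5 if withdrawal is driven by the recommendation. The figure of 0.5 should not be read as a maximum. The number of no-shows affected by the letter rule is small but cannot be derived from the documents.

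No endpoint or estimate changes: 10.4 removes formal withdrawers from the analysis datasets, and the letter rule has no bearing on the primary agreement analysis, whose data are the two recommendations. This is worth making at the next amendment and is not a reason to hold the trial.

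**What to change.** **Section 5.4.** In the sentence that triggers the missed-biopsy letter, insert *the in-person dermatologist or* before the mention of the teledermatology team. Correct the supplement letter cited there at the same time.

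**Section 7.3.5.** Keep the existing sentence for biopsy aftercare and add: *Participants who withdraw with a recommended biopsy not yet performed will also be offered the referral to the NYU Skin & Cancer clinic; section 5.7.2 continues to apply.*

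**Cost.** Wording in two sections, subject to the usual IRB review of amendments, and a handful of extra letters and referral offers over the trial. The referral and the letter already exist, and no visit or procedure is added. A referral is only an offer, so it respects the decision to withdraw. The case report forms are not shown, so whether a field would need changing cannot be checked.

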#### **7.3.6 Unscheduled Visit**

Participants may call and report a concern or adverse event at any time during the study duration. The most likely reason for an unscheduled visit would be related to poor wound healing. The DCSU staff will handle the questions and refer to one of the study physicians as needed. The participant may be asked to come to the DCSU in for an in-person evaluation and management. The most likely management outcome if wound infection is suspected would be providing antibiotic ointment to the participant. Unscheduled visits will be recorded in a separate field in the participant's case record form.

### **8 Assessment of Safety**

#### **8.1 Specification of Safety Parameters**

- Safety parameters are not included in primary or secondary endpoints
- Safety parameters to be recorded include participant adverse reactions to the imaging with the Nevisense device, as well as any adverse events recorded during intermediate, unscheduled or final study visits as reported by participants
- Any new onset symptoms, signs, illness or experience during the participant duration of the study will be recorded, quality of new onset signs, symptoms, illness or experience will be recorded

#### **8.1.1 Definition of Adverse Events (AE)**

An **adverse event** (AE) is any symptom, sign, illness or experience that develops or worsens in severity during the course of the study. Intercurrent illnesses or injuries should be regarded as adverse events. Abnormal results of diagnostic procedures are considered to be adverse events if the abnormality:

- results in study withdrawal
- is associated with a serious adverse event
- is associated with clinical signs or symptoms
- leads to additional treatment or to further diagnostic tests
- is considered by the investigator to be of clinical significance

#### **8.1.2 Definition of Serious Adverse Events (SAE)**

##### **Serious Adverse Event**

Adverse events are classified as serious or non-serious. A **serious adverse event** is any AE that is:

- fatal
- life-threatening
- requires or prolongs hospital stay
- results in persistent or significant disability or incapacity

- a congenital anomaly or birth defect
- an important medical event

that is caused by, or associated with, the study agent, if that effect, problem, or death was not previously identified in nature, severity, or degree of incidence in the investigational plan or application (including a supplementary plan or application). Important medical events are those that may not be immediately life threatening, but are clearly of major clinical significance. They may jeopardize the subject, and may require intervention to prevent one of the other serious outcomes noted above. For example, drug overdose or abuse, a seizure that did not result in in-patient hospitalization, or intensive treatment of bronchospasm in an emergency department would typically be considered serious.

All adverse events that do not meet any of the criteria for serious should be regarded as **non-serious adverse events**.

### 8.1.3 Definition of Unanticipated Problems (UP)

#### Unanticipated Problems Involving Risk to Subjects or Others

Any incident, experience, or outcome that meets all of the following criteria:

- Unexpected in nature, severity, or frequency (i.e. not described in study-related documents such as the IRB-approved protocol or ICF, the investigators brochure, etc.)
- Related or possibly related to participation in the research (i.e. possibly related means there is a reasonable possibility that the incident experience, or outcome may have been caused by the procedures involved in the research)
- Suggests that the research places subjects or others at greater risk of harm (including physical, psychological, economic, or social harm).

This definition could include an unanticipated adverse device effect on health or safety caused by, or associated with, a device, if that effect, problem, or death was not previously identified in nature, severity, or degree of incidence in the investigational plan or application (including a supplementary plan or application).

## 8.2 Classification of an Adverse Event

### 8.2.1 Severity of Event

For AEs not included in the protocol defined grading system, the following guidelines will be used to describe severity.

- **Mild** – Events require minimal or no treatment and do not interfere with the participant's daily activities.
- **Moderate** – Events result in a low level of inconvenience or concern with the therapeutic measures. Moderate events may cause some interference with functioning.
- **Severe** – Events interrupt a participant's usual daily activity and may require systemic drug therapy or other treatment. Severe events are usually potentially life-threatening or incapacitating.

### 8.2.2 Relationship to Study Agent

*The clinician's assessment of an AE's relationship to study agent (device) is part of the documentation process, but it is not a factor in determining what is or is not reported in the study. If there is any doubt as to whether a clinical observation is an AE, the event should be reported. All AEs must have their relationship to study agent assessed. In a clinical trial, the study product must always be suspect. To help assess, the following guidelines are used.*

- **Related** – *The AE is known to occur with the study agent, there is a reasonable possibility that the study agent caused the AE, or there is a temporal relationship between the study agent and event. Reasonable possibility means that there is evidence to suggest a causal relationship between the study agent and the AE.*
- **Not Related** – *There is not a reasonable possibility that the administration of the study agent caused the event, there is no temporal relationship between the study agent and event onset, or an alternate etiology has been established.*

### 8.2.3 Expectedness

Principal Investigator [name] will be responsible for determining whether an AE is expected or unexpected. An AE will be considered unexpected if the nature, severity, or frequency of the event is not consistent with the risk information previously described for the study procedures. The expected AE's for the Nevisense device have been described in FDA clearance documents. There are no expected AE's for the clinical and dermoscopic imaging.

